3. STUDY DESIGN

This study is a decentralized, prospective, observational study with 15 weeks follow-up (Figure 1). The study will be performed in two different populations-participants with COPD and participants with PD. Participants will go to their assigned local physiotherapy practice 4 times (once every 5 weeks) for in-clinic assessments of walking capacity and disease symptoms (specific to COPD and PD cohorts), while wearing three (3) different wearable sensor devices-the Verily Study Watch on one wrist, Fitbit Sense on another wrist and Modus StepWatch on the ankle. After each visit, participants will also fill out questionnaires on motor symptoms, cognition, quality of life, activities of daily living, and fatigue. In addition to wearing the Verily Study Watch for 23 hours per day and StepWatch device for two weeks of the study, at least 4-6 hours per day, between Visits 2 and 4 (and a Fitbit device for the participants who agree to do so, for the first 5 weeks, 23 hours per day of the study participation,), participants will be instructed to perform weekly home assessments (i.e. 6MWT and TUG tests). These assessments will be guided by the graphic user interface on the Verily Study Watch. Between week 5, and the end of the study (week 15), participants will participate in 10 weeks of physiotherapy treatment including a high-intensity aerobic exercise component. The intervention is hypothesized to impact walking capacity and induce variation in walking test scores. In the first 5 weeks of the trial, physiotherapy is allowed, only when deemed necessary by the patient and physiotherapist. Patients will not receive high-intensity aerobic exercise training during this period.

Estimated study timelines:

First Participant enrolled: December , 2021

Enrolment Period: 18 months

Follow-up duration: 15 weeks per participant

[figure not shown]
Total study duration: 30 months

Data cleaning/closeout: 3 months

[figure not shown]
End of study: July 2024

Figure 1. Study Design

COPD arm

PD arm

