In-Clinic Portion: Participants will come to their assigned local physiotherapy practice four times (once every five weeks) for in-clinic assessments of walking capacity, and will be instrumented with up to three sensor wearable devices (Verily Study Watch, Modus StepWatch 4, and the Fitbit Sense) during the assessments. Participants will undergo a 10-week high intensity exercise training program supervised by a specialized physiotherapist as an intervention.

Remote Portion: Participants will be instructed to wear the Verily Study Watch for up to 23 hours per day for the entire study duration (15 weeks), to enable continuous free-living data collection, and will be asked to perform the Six-Minute Walk Test (6MWT) and Timed Up and Go test (TUG) once a week using the Verily Study Watch. Verily Study Watch will send out notification to perform 6MWT and TUG and guide participants through the remote assessments. A subset of participants may also wear the Fitbit Sense concurrently with the

Study Watch and will be asked to wear them for the first 5 weeks between first and second visits. All COPD and PD participants will also wear the Modus StepWatch 4 concurrently with the Study Watch for 14 days between week 5 and week 15. During these 14 days, participants are asked to wear the StepWatch for at least 10 days, which can fall on any random day with a minimum of two weekend days. Wear time of four to six hours on these days is intended.

Patients who are on a physiotherapist-supervised maintenance program with only low-frequency sessions (maximum 1 session per week) prior to study entry may continue during the first 5 weeks of the study (the baseline period). Newly referred patients will be asked to start intensive physiotherapy after the 5 week baseline period. However, if the participant and the physiotherapist think it is necessary or needed, it is allowed to start physiotherapy with a low frequency (maximum 1 session per week) during the baseline period. Five weeks of baseline period will allow to capture variability/fluctuation in symptoms, functional physical capacity, and other characteristics in participants activities of daily living based on sensor recorded data. Ten weeks of high intensity physiotherapy intervention is expected to induce changes in functional physical capacity and we will assess whether we can capture these changes using sensor data.

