Simultaneous wear of the StepWatch along with Study Watch on the ankle and wrist, respectively, for at least 2 weeks during the study, will be an additional burden. However, the StepWatch does not require any form of interaction (i.e., no charging / syncing) The Verily Study Watch is being used in another study in participants with PD and the participants showed excellent compliance,⁴ therefore it is expected that this will be a realistic approach. Participants will wear three different wearable devices in the clinic and max two devices at home. In the clinic, participants will wear the Study Watch on one wrist, Fitbit Sense on the other wrist, and the Modus StepWatch on the ankle for the duration of clinic visits for all four visits. For those who are willing to wear the optional FitBit device at home (minimum 50 people with COPD and 30 people with PD), simultaneous wear of the devices on each wrist, for at least the first five weeks of the study duration, will be an additional burden. However, participants will only wear a maximum of two devices at home simultaneously, even when the participant chooses to wear optional Fitbit device, because the timing of each device wear during study is different (i.e., Fitbit will be given for the first five weeks, and StepWatch will be given after the first five weeks). It is expected that this would be feasible based on prior studies where multiple devices were required to be worn for prolonged periods of time for the people with COPD⁴ and PD.⁵⁻⁷ In addition, wearing FitBit is not an obligatory part of the study, and participants can decline wearing multiple devices at the same time at home.

The main risks related to the safety of performing an unsupervised (submaximal) aerobic exercise test at home are related to falls and cardiovascular events. Falls may be more frequent in the PD population, while cardiovascular risk is higher in COPD because of (potentially undiagnosed) cardiovascular comorbidity. Risks associated with home measurement will be minimized by excluding participants that have fallen more than once in the last three months and by asking the treating physician (i.e. general practitioner, pulmonologist or neurologist) to assess a person's ability to participate in this study. Finally,

participants will receive 10 weeks of personalized physiotherapy, which they would also receive if they would not participate in this study.

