2.2 Secondary objectives

For COPD:

- 1) To analytically validate algorithms that utilize free living data to estimate the outcome of in-clinic Timed-up-and-go test (TUG) and obtain analytical validation of the algorithms;
- 2) To analytically validate algorithms that utilize virtual TUG to estimate the outcome of in-clinic TUG and obtain analytical validation of the algorithms;
- 3) To evaluate analytical validity of algorithms capturing various aspects of walking that utilize passively recorded sensor data; and
- 4) To obtain test-retest reliability of the following algorithms based on weekly Virtual 6MWT between first and second visits:
 - Free-living data based 6MWT distance estimator
 - Virtual 6MWT distance estimator
 - Free-living data based TUG time estimator
 - Virtual TUG time estimator.
 - Free-living walking measurements

A small set of pre-selected data will be used to refine the algorithms that are mainly developed using data from other sources.

For PD:

- 1) To obtain the dataset to develop algorithms that utilize free living data to estimate the outcome of in-clinic Timed-up-and-go test (TUG); and

- 2) To obtain the dataset to develop algorithms that utilize virtual 6MWT context-known data to estimate the outcome of in-clinic Timed-Up-and-Go test (TUG).
- 3) To obtain the dataset to evaluate analytical validity of free-living walking measurements utilize passively recorded sensor data.

COPD and PD participants will wear StepWatch and Study Watch at home over two weeks. This will provide a dataset to compare free-living data based walking measurements by the two devices. StepWatch will be used as a reference device to evaluate the performance of Study Watch walking measurements to quantify waking activity and walking capacity in at home settings.

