- About 80% of participants will have sufficient data for the final algorithm assessment. (This takes into consideration participants' drop outs (20%), sensor data of insufficient quality to generate reliable algorithm outputs, and failure to obtain the ground truth labels (e.g. step watch errors).

The table below illustrates the power achieved by the algorithm for the best performing metrics assuming N=100 (including 20% drop-out) and a type I error of 0.05. This suggests that N=100 participants with StepWatch at home data will provide moderate power with given success criteria and current performance for some metrics to assess the analytical validity of these metrics as secondary endpoints.

Table 2: Power Analysis with Various success criteria, for n=100

Walking Suite Measures	Success criteria (from literature)	Current Performance	Power achieved(%)
Cadence 95 percentile	>0.82	0.88	0.64
Bout cadence 75 percentile	> 0.75	0.82	0.51
Cadence 75 percentile	>0.7	0.77	0.4
Number of Bouts	>0.66	0.7	0.17

For the optional part of the study (i.e. wearing the Fitbit at home) we only defined minimum numbers (for Fitbit, 50 COPD and 30 PD) and have not defined a maximum number of participants and aim to include as many participants as possible beyond the minimum numbers.

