Except in the case of the Virtual Walk tests, and performance and event tagging, the device requires no other user intervention to capture or analyze physiological data and collects data passively with minimal information communicated to the user via the device (i.e., date and time, charge status, sync status when connected for data transfer). Participants' button press inputs marking the beginning and end of each walk test will be used to determine the onset and offset of the test in the sensor data. Medication tagging will be used to understand manifestation of medication on and off states in the sensor measurements for PD patients.

The Study Watch has been carefully designed to use current technologies (e.g. virtually continuous data collection) to investigate physiological and environmental variables that may shed light on the evaluated disease, its progression, and response to therapy when combined with other clinical variables collected during the study.. Since it is intended for research only and it is not CE marked, approval from a competent authority in the Netherlands will be obtained for use of this investigational device for this Accuracy of Digital Assessment of Performance Trial. We have previously obtained approval for using the Study Watch in the context of the Personalized Parkinson Project (registered under file VGF2002688).

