7. NON-INVESTIGATIONAL PRODUCT

7.1 Fitbit Sense and Fitabase

Fitbit Sense is a wrist-worn wearable consumer electronics device (CE marked in EU, made by Fitbit). Fitabase is a third party software that allows access to fitbit data for clinical research purposes masking sensitive information, and providing de-identification (pseudonymization). Fitbit's on-board sensors collect data that may include movement and activity, pulse rate, electrodermal activity (EDA), electrocardiogram (ECG), and on-skin temperature. The device also provides a variety of wellness metrics related to activity level, pulse rate, heart rate, heart rate variability, oxygen saturation and sleep on the device and through mobile application. Fitbit Sense may collect geolocation data if users turn on activity labeling features outdoors (like manually selecting a jogging activity on the watch activity labeling menu) but this data will not be accessible by site staff nor researchers. The entire

data types that are collected and accessible from Fitbit are listed in Appendix A. The Fitbit sense device in this investigation is being used within the intended purpose for which CE marking was issued.

Data from the device is transferred to Fitbit's database through Fitbit's mobile application (from the device to the mobile application via bluetooth connectivity and from the mobile application to Fitbit's database via WiFi or cellular connectivity). Researchers and site staff at Radboud may access the aggregated data using Fitabase (a third party provider that allows access to de-identified Fitbit Data for research purposes) , but to ensure strict adherence to current regulations, no data transfer will be made from Radboud to Verily. Verily must set up an appropriate Access Restricted Data Store (ARDS). Verily will be able to access the data only through an Access Restricted Data Store (ARDS) that will receive data from Radboud via the Fitabase platform.

For the current study, access will be limited to aggregated data and derived metrics (e.g., step counts, sleep duration, etc.) based on raw data recorded using Fitbit's accelerometer, gyroscope, and photoplethysmography sensors. These metrics will be used for algorithm development and comparison with metrics derived from Study Watch sensor data. Verily will not have access to other types of sensor data or participant location data, as these will be masked by Fitabase.

7.2 Modus StepWatch 4

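### Home Fitbit wear puts visible activity feedback in the baseline weeks only and in volunteers only, and the plan neither limits that feedback nor checks its effect on free-living measures

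*Combined protocol and SAP*

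**What the plan says.** - **Who wears the Fitbit at home, and when.** Section 3 gives the device to those who agree: "a Fitbit device for the participants who agree to do so, for the first 5 weeks". Section 8.3, the assessment table in that section, and section 8.5 also place home wear between Visits 1 and 2. The Summary (burden paragraph) separates the devices in time: "Fitbit will be given for the first five weeks, and StepWatch will be given after the first five weeks". The same paragraph also describes simultaneous wear "for at least the first five weeks of the study duration", which leaves longer wear open.
- **How many.** Section 4.4 sets minimums of 50 COPD and 30 PD participants. It adds that the investigators "have not defined a maximum number of participants and aim to include as many participants as possible beyond the minimum numbers".
- **What the wearer sees.** Section 7.1 says of the Fitbit Sense: "The device also provides a variety of wellness metrics related to activity level", among other measures, both on the wrist and in the app. Section 4.2 requires home wearers to own a smartphone and install that app. The Study Watch, worn throughout, "collects data passively with minimal information communicated to the user via the device" (section 6.1.1). The Summary says the StepWatch needs no interaction.
- **What the baseline weeks are for.** Section 2.2 takes COPD test-retest reliability "based on weekly Virtual 6MWT between first and second visits", and its list includes the two free-living estimators and the free-living walking measurements. The Summary uses the five weeks to capture fluctuation in daily life. It expects training to change functional capacity and says "we will assess whether we can capture these changes using sensor data".
- **What controls it.** Section 8.12 names compliance, fatigue and learning as the main factors considered, not activity feedback. Section 10 has no analysis by Fitbit wear.

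**The concern.** Free-living measurement is meant to show usual behaviour. A participant who can read an activity count may walk differently. Here that possibility arises in one period and not the next, and in people who chose the device. Training starts as the Fitbit is handed back, so in wearers any feedback effect is confounded in time with the start of the intervention.

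Three things could be touched: baseline free-living measures as a description of usual walking, the comparison of baseline with training weeks that the Summary has in mind, and test-retest results from the same weeks. A larger sample would not remove the bias, because exposure depends on period and on volunteering rather than on chance.

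**Working it through.** The plan states no figure on this point, so there is none to reproduce. The check is a set of shares, an illustration under stated assumptions, and a look at each analysis in turn.

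**1. Share exposed (sections 4.1 and 4.4).** Share = minimum home wearers / cohort size.
- COPD: 50/200 = 25%.
- PD: 30/130 = 23%, or 30/100 = 30%, since section 4.4 plans for 100 and section 4.1 allows up to 130.
- There is no cap, so both shares could be much higher. After week 5 the planned share is 0%.

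**2. Shift in mean baseline walking.** The documents give no feedback effect, so the effect r in a wearer is an assumption. Shift = share × r.
- At a 25% share: r = 5%, 10%, 20% gives 1.25%, 2.5%, 5%.
- At a 50% share: 2.5%, 5%, 10%.
- If r = 0 there is no shift; if r is negative the shift is downward.

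**3. Change from baseline to training.** Assumptions: a free-living activity measure truly rises by g = 15% in everyone; feedback acts throughout weeks 0-5 and disappears when the device is returned. Wearer's apparent change = (1 + g)/(1 + r) − 1. Cohort average = p × wearer change + (1 − p) × g, with p the share of wearers.

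| Assumed r | Wearer | Cohort, p = 25% | Cohort, p = 50% |
|---|---|---|---|
| −5% | +21.1% | +16.5% | +18.0% |
| 0 | +15.0% | +15.0% | +15.0% |
| 5% | +9.5% | +13.6% | +12.3% |
| 10% | +4.5% | +12.4% | +9.8% |
| 20% | −4.2% | +10.2% | +5.4% |

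For example, at r = 10%: 1.15/1.10 − 1 = 4.5%, and 0.25 × 4.5% + 0.75 × 15% = 12.4%. The table shows how sensitive such a comparison would be. It does not estimate what will happen.

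**4. Test-retest.** Write a wearer's week-t value as true level + d(t) + error. The difference between weeks s and t contains d(t) − d(s). A home wearer has the Fitbit for the whole window, so a steady effect cancels and adds no within-person error. Only an effect that builds or fades over the five weeks adds disagreement. A steady shift in some participants can alter between-person spread, and so a pooled coefficient, but that is not a loss of repeatability.

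**5. Other analyses.** The co-primary ICCs (section 10.2) compare estimated with in-clinic 6MWT distance and do not involve change in activity. Free-living estimates paired with early visits could be touched, but probably little. The virtual tests are prompted tasks and less exposed. Home StepWatch wear falls between Visits 2 and 4, when no home Fitbit is planned, so that comparison is untouched.

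**The case against.** The strongest reply is that section 10 contains no baseline-to-training analysis. The aim rests on a Summary sentence about functional capacity, and the Summary and section 1 treat capacity and activity as distinct. Activity volume is nowhere named as a change outcome. This stands: what is at risk is a stated aim without a specified analysis, not a formal endpoint.

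The size of any bias is assumed throughout, and this also stands. A reader might infer that the Fitbit will inflate baseline walking and hide the training effect. The documents do not show that feedback changes walking in these participants, in which direction, or by how much. The negative value in the table follows from choosing r = 20%.

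A reader might also infer that the test-retest results or the primary validation are compromised. Steps 4 and 5 of the working do not support that.

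The timing has a reason: the Summary limits home wear to two devices at once. That explains the schedule but does not deal with the feedback. Section 8.3 records the wearing hand for each device and section 10.4 summarises device-use compliance, so wearers should be identifiable, yet no analysis uses this. The masking in section 7.1 governs what researchers and the device company can access, not what the wearer sees. The separate Fitbit instructions may cover display settings, but they are not part of these documents.

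**Conclusion.** The point holds in a limited form. Activity feedback visible to the wearer is voluntary, uncapped and planned for weeks 0-5, in at least 25% of COPD and 23-30% of PD participants, while the other home devices give little or none. If feedback changes walking, baseline free-living measures in wearers, and any comparison of those weeks with training, could be biased. Week-to-week reliability is affected only if the effect varies within the five weeks. Size and direction are unknown.

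The shares rest on the plan's own minimums. The confinement to baseline rests on the five-week wear stated in most places, which the one looser phrase in the Summary leaves unsettled. The co-primary conclusions are not in question. The case for acting is that the remedy is cheap and the cross-device aim in section 2.3 needs concurrent recordings, not a display that the participant can read.

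**What to change.** 1. **Sections 8.3 and 8.5.** Set up home Fitbits so that activity metrics, goals and movement prompts are off or hidden as far as the device allows, and ask wearers to use the app only to sync. Confirm that the data in Appendix A are still recorded. Cost: a set-up line in the site instructions and possibly lower uptake of the optional device.
2. **Sections 10.3 and 10.4.** Define a participant-level flag for home Fitbit wear. Prespecify a sensitivity analysis that reports free-living test-retest results, and any baseline-to-training analysis of free-living metrics, for all participants and separately by home Fitbit wear. Keep the all-participant analysis as the main one whatever the result, and state that wearers are self-selected, so a difference may reflect selection as well as feedback. Cost: one extra analysis with smaller subgroups.
3. **Do not switch to the analysis without wearers if results differ.** That rule depends on the data, replaces possible feedback bias with a selected sample, and fails at high uptake: 25% of the COPD cohort is lost at the minimum, half at 50% uptake.
4. **Summary.** Reconcile the phrase that leaves wear beyond five weeks open with the five-week period stated elsewhere.

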4. STUDY POPULATION

4.1 Population (base)

Two hundred (200) participants with COPD and up to 130 participants with PD who have been referred to a physiotherapist will be enrolled. Both cohorts of participants (COPD and PD) are expected to have reduced 6MWT distance outcomes that correlate with disease severity. However, due to the different underlying mechanisms of the diseases, the reasons for changes to the 6MWT distance may be different (i.e., pulmonary obstruction and overall limitation of the cardiovascular for people with COPD vs. reduced walking capacity and mobility for the people with PD due primarily to neurological impairment). In order to develop algorithms that will work across multiple root causes for functional capacity reduction, two different populations, COPD and PD, are selected. Different sets of features will be identified from each group to assist in developing algorithms with suitable performance for both conditions. These conditions are expected to be exemplary for other pulmonary, cardiovascular or neurological conditions as we look to expand the usage of developed algorithms across more indications.

